In our implementation of MixR, a user is able to simultaneously and directly view a patient and a reference hologram of their external surface derived from their initial planning CT scan. The hologram provides a visual reference for the exact posture needed during treatment and is initialized in relation to the origin of the RT device. Thus, by matching a patient to their hologram, the correct posture is achieved while subsequently registering the patient with the RT device. This is highly relevant in breast RT where setup is challenged by the independent movement of local anatomy and the deformability of pendulous breasts. Such a system removes the need for expensive and restrictive external

cameras and holds the promise to improve outcomes by improving accuracy and safety while reducing both setup time and imaging dose. By designing an application for a commercial off-the-shelf device with a cost of less than \$4,000, we also believe the method capable of improving portability, reducing cost, and increasing accessibility for centers with limited resources. We have developed an initial version of this application using the HoloLens v2 and collected preliminary data using phantoms. The data supports an overall alignment accuracy of 3-4 mm.

The purpose of the current research is to extend this testing to patients by performing a pilot study to assess the accuracy, overall setup time, and amount of IGRT needed when utilizing MixRT for patient setup in breast RT. Comparisons will be made between MixRT and 3-point alignment for 3D conformal photon treatment, and MixRT/IGRT versus IGRT alone for pencil beam scanning proton treatment. This data will be used to establish viability and provide the framework for larger comparative effectiveness research studies and eventual FDA clearance.

4.) Background:

Radiotherapy workflow

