Figure 2. System for patient alignment via hologram: A) Initial simulation CT scan, B) Creation of 3D object file from body contour, C) Development platform where patient isocenter is linked with virtual representation of physical marker, D) Physical marker attached to machine at pre-determined location linking patient isocenter with radiation isocenter; patient hologram (blue) is visualized through HoloLens v2 highlighting the mis-alignment of the mannequin (white), E) Physical mannequin adjusted to match the reference hologram, thus reproducing the required posture and registering the mannequin with the RT device.

Table 1. Preliminary accuracy of MixRT for rigid alignment.

	User 1	User 2	User 3	Mean	StDev
Shift (mm)	n = 5				
Vrt	0.8	0.6	1.5	1.0	0.8
Lng	1.1	1.3	1.2	1.2	0.7
Lat	2.0	1.8	2.4	2.1	1.5
RMS	2.4	2.6	3.3	2.8	1.4
Shift (°)	n = 15				
Rtn	0.4	0.7	0.7	0.6	0.6
Pitch	0.1	0.1	0.0	0.1	0.1
Roll	0.1	0.1	0.1	0.1	0.1

[figure not shown]
In preparation for this study, we have developed a preliminary application to enable MixRT and provide initial estimates of hologram stability, alignment accuracy, and user variability. In one experiment, three users were tasked with aligning a rigid anthropomorphic phantom with an RT device (linear accelerator) while wearing the HoloLens v2. Each user performed the alignment five times, and accuracy was quantified using IGRT.

For each user, all five measurements were completed within the same session. Between measurements, the setup was disassembled and reset. The results shown in Table 1 preliminary estimate an overall accuracy of 3 ± 1 mm. These results were consistent between all users across all sessions. Considering the preliminary nature of the study, these results

are extremely encouraging, achieving less than the 5 mm alignment tolerance for 3D photon treatments and approaching the 2 mm alignment tolerance for proton treatments.

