- **Describe the inclusion and exclusion criteria for this project:** This study will target adult patients who are planning to undergo photon or proton radiation therapy at UFHPTI for treatment of the breast or chest wall. As this type of treatment is rare in men, the study will focus on female patients only.
- **Provide a thorough step-by-step description of what you intend to do throughout the course of the study in a logical and sequential format:**

Hologram creation

For all patients included in this study, we will create holograms based on the external body contour derived from their planning CT dataset. This contour is routinely segmented during treatment planning; thus, we will only need to access the existing contour located in the software system MimVista and export it to our software system. We will also access patient setup photos located in a clinical file system and export these to our application.

Mixed-reality guided patient setup

At UFHPTI, we treat breast/chest wall patients using various modalities and techniques. In all cases, patient setup begins with a 3-point alignment. The additional use of IGRT depends on modality, approach, and patient-specific variables. Most patients treated with 3D conformal photon therapy (3DCRT) receive only weekly IGRT, including kV orthogonal and MV portal imaging. The 3-point alignment, thus, represents the standard setup for the majority of treatment, both here and across the nation, as 3DCRT is the most common technique for breast RT. As such, one of our primary aims is to pilot the clinical implementation of MixRT with the goal of accuracy similar to or better than a traditional breast setup involving 3-point alignment (5mm tolerance).

We will recruit 12 patients scheduled to receive whole breast or chest wall RT using a supine, 3DCRT or IMRT approach. All patients will be consented for a study comparing the accuracy of MixRT with a traditional 3-point alignment as quantified using CBCT. To control for setup variation which typically decreases after the first few treatment fractions, we will stratify patients into two groups using an alternating method. In the first group, the therapists will position the patient using 3-point alignment during fractions 1-5 (5 total), then using MixRT for fractions 6-10 (note:

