- **Briefly outline the data analyses that are proposed and who will do the analysis:** Mean estimates and associated 95% confidence intervals will be attained for registration error and registration time for the mixed reality and standard of care methods and the paired difference of the two techniques. We will assess feasibility using a paired T-test. The hypothesis is that the mean paired differences across all measures of registration error and registration time are not significantly different than 3 mm and 5 minutes, respectively. The number of CBCTs collected as part of the registration process will be assessed subjectively since count data are not truly continuous. This analysis will be carried out by the study investigator and study statistician.
- **Describe your plan for conducting interim analysis. What stopping rules are in place?** N/A.

8.) Data Safety and Monitoring Plan:

- **Is there a Data Safety Monitoring Board (DSMB) or an oversight committee for this research project?** The UF Data Integrity & Safety Committee will provide oversight through annual monitoring.

- **Describe your plans for monitoring study conduct and subject safety:** The Principal Investigator will be responsible for monitoring.
- **Provide Information about the DSMB or committee including who is on the committee, how frequently will the committee meet, and when will you get information from the committee:** N/A

9.) Possible Discomforts and Risks:

- **Identify all discomforts and risks (physical, psychological, social, and/or economic) study participants may encounter, listing more common risks first and less common risks separately:** Based on prior study utilizing anthropomorphic phantoms, we anticipate that our patient alignment system will ultimately reduce setup time and the number of X-ray images used for alignment. We have yet to try this with patients, however, and there is a risk that it could marginally increase setup time, at least during the initial implementation.

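### Photon accuracy is tested only as a MixRT-minus-standard difference against an unexplained 3 mm, and the 5 mm tolerance in the photon goal is never used

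*Combined protocol and SAP*

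**What the plan says.** Section 7 (Statistical Analysis) plans means with 95% confidence intervals for each method and for their paired difference. Feasibility is then judged by a paired t-test of the hypothesis that the "mean paired differences across all measures of registration error and registration time are not significantly different than 3 mm and 5 minutes, respectively". It does not say whether 3 mm is a gain or a loss, why it was chosen, or whether photon and proton patients are analysed separately.

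Elsewhere, figures of this size describe MixRT alone. Section 4 (MixR-Guided RT) says that the phantom results "preliminary estimate an overall accuracy of 3 ± 1 mm", and the Abstract says "The data supports an overall alignment accuracy of 3-4 mm". Section 4 compares the phantom result with absolute limits, "achieving less than the 5 mm alignment tolerance for 3D photon treatments and approaching the 2 mm alignment tolerance for proton treatments".

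For photons, Section 6 (Mixed-reality guided patient setup) sets the goal as "accuracy similar to or better than a traditional breast setup involving 3-point alignment (5mm tolerance"). The cohort is small: "We will recruit 12 patients scheduled to receive whole breast or chest wall RT". Each patient has five fractions per method.

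**The concern.** The photon goal combines two questions: is MixRT comparable with 3-point alignment, and is its error acceptable against 5 mm? Section 7 tests only a difference, and the number it uses is as large as the entire error expected of MixRT. A difference that size is hard to call comparable accuracy. A difference also says nothing about the absolute error unless the comparator's error is known, and the documents do not give the 3-point error in patients. The trial could therefore meet its stated benchmark while MixRT's mean error lies above the tolerance named in its own goal.

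This is separate from the direction of the test. If the hypothesis were turned into a proper one-sided bound, the 3 mm would still need a reason.

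**Working it through.** **Inputs from the documents.** Table 1 row "RMS 2.4 2.6 3.3 2.8 1.4" (three users, mean, SD); photon tolerance 5 mm; benchmark 3 mm; n = 12 photon patients. The plan gives no power calculation to reproduce.

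**Assumptions.** Two-sided 5% level, inferred from the 95% intervals; one value per patient; normal patient-level values. The 3-point mean in patients and the SDs are not given, so ranges are shown.

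**Size of the benchmark.** Mean of the three users: (2.4 + 2.6 + 3.3)/3 = 2.77, which agrees with the 2.8 mm in Table 1. Then 3/2.8 = 107% of MixRT's phantom error, and 3/5 = 60% of the photon tolerance. The benchmark also exceeds each single-axis phantom mean (1.0, 1.2 and 2.1 mm).

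**The rule as written.** A true mean loss of exactly 3 mm is the hypothesised value, so a two-sided 5% test retains it 95% of the time, whatever the SD. MixRT's mean is then the 3-point mean + 3 mm, which exceeds 5 mm whenever the 3-point mean exceeds 5 - 3 = 2 mm.

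**A rewritten rule.** Suppose passing means that the upper 95% bound of the mean paired difference is below 3 mm. For a true loss d,

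P(pass) = 1 - F(t; 11, λ), with t = t(0.975, 11) and λ = (3 - d)√12/SD,

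where F is the noncentral t distribution function. A 50% worsening is d = 0.5 × the 3-point mean.

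| 3-point mean, assumed (mm) | MixRT mean (mm) | 3 - d (mm) | SD 1.4 | SD 2 | SD 3 |
|---|---|---|---|---|---|
| 3 | 4.5 | 1.5 | 92% | 66% | 35% |
| 4 | 6.0 | 1.0 | 62% | 35% | 18% |
| 5 | 7.5 | 0.5 | 20% | 12% | 8% |

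The pass rate is above one half only if the SD is below about 2.4, 1.6 and 0.8 mm respectively.

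The phantom SD of 1.4 mm is a spread over 15 setups, not a paired SD between patients. Phantom noise alone, for a difference of two five-fraction means, would give 1.4 × √(2/5) = 0.89 mm; variation between patients would add to that.

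**Checking MixRT's own mean against 5 mm.** The same formula applies with 5 minus the true MixRT mean in place of 3 - d, and SD now the between-patient SD of MixRT's patient means.

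| True MixRT mean (mm) | Gap to 5 mm | SD 1.4 | SD 2 | SD 3 |
|---|---|---|---|---|
| 3 | 2 | 99% | 88% | 56% |
| 4 | 1 | 62% | 35% | 18% |

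The two rows are the ends of the 3-4 mm range in the Abstract.

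**The case against.** The best defence is that Section 7 never calls 3 mm a margin, so pass rates for an upper-bound rule describe a test that the plan does not contain. This is correct. Under the rule as written, a true 1.5 mm worsening is retained 0.3%, 34% and 65% of the time at SD 1, 2 and 3 mm. The table above shows only that repairing the form of the test would not by itself make 3 mm informative.

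Three stronger readings are tempting, and the documents do not support them.

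- *A setup error 50% worse would usually pass.* That depends on a 3-point error and an SD that the documents do not give. At SD 2 mm it is true for a 3-point mean of 3 mm and false for 4 or 5 mm. Where it is true, the MixRT mean of 4.5 mm is still within tolerance.
- *The benchmark contradicts the plan's own figures whichever way it is read.* As a tolerated loss, it would need a 3-point mean of 2.8 - 3 = -0.2 mm to be reached at MixRT's phantom error. That shows only that expected performance lies inside the benchmark. As an expected gain, it implies a 3-point mean of 2.8 + 3 = 5.8 mm. A tolerance does not cap mean uncorrected error, and Section 4 reports a standard mannequin setup with a 2 cm arm difference. The gain reading is plausible: the accompanying 5 minutes equals the 11-to-6-minute reduction cited in Section 4, although the plan makes no such link.
- *A 2 mm margin follows from 5 mm minus 3 mm.* This applies absolute headroom to a difference. With 3-point alignment at 4 mm, a 2 mm loss gives 6 mm, which is again over tolerance.

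Two further points stand. The plan already reports an interval for each method, and it openly describes itself as an underpowered pilot. Nor is this a claim of patient harm: study setups are verified by CBCT, and Section 6 says that final positioning follows IGRT.

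**Conclusion.** The point holds in limited form. The only accuracy criterion is a difference against 3 mm, without direction or reason, at about 107% of MixRT's phantom error and 60% of the photon tolerance. The tolerance in the photon goal plays no part in the analysis. That follows from the text and simple arithmetic. It needs no assumption about patients beyond the 5% level behind the 95% retention figure.

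How often a materially worse setup would get through a corrected 3 mm test cannot be fixed from the documents. Over the ranges in the table it runs from 92% to 8%. Pilot status excuses the lack of power. It does not excuse a criterion that leaves half of the photon goal unaddressed when the needed interval is already planned. This is a worthwhile, inexpensive improvement; it does not invalidate the study.

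**What to change.** In Section 7, for the photon cohort:

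1. Compute one mean 3D translational error per patient and method over that method's fractions. Report rotations separately, since a millimetre figure cannot apply to them.
2. Compare the upper 95% confidence bound of MixRT's own mean with the 5 mm tolerance.
3. Report the MixRT-minus-3-point paired difference as an estimate with its 95% interval. Do not use 3 mm as the pass mark for comparable accuracy unless the sponsor states its direction and justifies it on the difference scale. No specific replacement margin follows from the documents.

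The cost is a change of wording, with no new patients or measurements. The downside is a stricter pass mark, as the last table shows. If MixRT's true mean in patients is 4 mm rather than 3 mm, a sample of 12 will often fail to place the bound below 5 mm, and the report should present that as imprecision rather than as evidence that MixRT is out of tolerance.

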16 fractions is a common course of breast RT). For the second group, we will reverse the order, using MixRT for fractions 1-5 and 3-point alignment for fractions 6-10. In this way, each patient will serve as their own control. In all cases, patient alignment will be verified using CBCT which will be registered to the simulation CT by the treatment therapists using the standard clinical workflow. The magnitude of the resulting shift will be recorded. If further adjustment is necessary, the number of repeated CBCTs will be recorded along with the shift magnitude. All registrations will be reviewed by a board-certified radiation oncologist (one of the co-investigators) who will qualitatively assess the accuracy of the setup while blinded to the setup method. The process for mixed-reality alignment is noted below:

1. Identify the patient and initialize their hologram by detecting a QR-coded cube attached to the treatment device.
2. Setup the patient according to their setup photos, related immobilization devices (typically only an inclined breast board), and 3-point alignment. Further match the patient to their hologram as viewed through the HoloLens 2 device.
3. Utilize IGRT to verify proper alignment per protocol or departmental standards.
4. Make corrections as needed based on IGRT.
5. Repeat steps 1-3 if necessary.

For patients receiving proton therapy, setup typically includes routine CBCT, the challenges of which were previously discussed for non-rigid alignment including prolonged setup time and increased imaging dose. The primary goal of this sub-aim is thus to show that MixRT can reduce setup time and the amount of imaging dose in cases requiring CBCT alignment. To evaluate this, we will recruit an additional 12 patients scheduled to receive RT using a supine, pencil-beam scanning approach. As with 3DCRT/IMRT approach, we will divide patients into two groups using an alternating method and alternate the setup approach between fractions 1-5 and 6-10, reversing the order between the two groups. Setup time will be tracked from the moment the patient lies on the treatment couch to when the final position is confirmed by the therapist prior to treatment. Patient alignment will be verified/quantified in a similar manner as noted above.

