A window period of 2 additional fractions is permissible for the collection of study data. This window period is provided to allow a patient to remain on study through her 12th fraction of treatment if the patient is not able to receive the study intervention during one to two of her first 10 fractions.

To summarize, we intend to enroll 12 patients receiving either 3DCRT or IMRT and 12 patients receiving proton therapy. Within each modality, patients will be randomized into two groups using an alternating method. The order in which MixRT will be utilized will be reversed between the groups. The measured data will include registration accuracy (6 DoF shifts), setup time, and number of CBCT's utilized. Registration accuracy will be quantified using the image registration module that is used as part of the IGRT process. Setup time will be quantified using a stopwatch.

The number of CBCT's will be quantified via counting the number that are used during the setup process. Patients receiving photon IMRT receive daily CBCT as part of the standard of care. Thus, this investigation would likely not introduce additional imaging dose for these patients. For proton therapy CBCT is used weekly, and for 3DCRT it is not routinely used. Thus, this investigation would represent a marginal increase in the utilization of CBCT for these patients, up to 10 extra CBCT's nominally.

Setup during Verification CT

Radiotherapy patients at UFHPTI often receive repeat CT scans (verification scans) at periodic timepoints during the course of treatment to assess for anthropomorphic changes that could have dosimetric effect. Reproducing the posture from the initial CT simulation is critically important yet difficult to achieve due to the lack of real-time feedback. For patients who receive a verification CT (likely all proton patients), we will implement holographic alignment during this process and assess its accuracy in comparison to CT acquisition without the aid of holographic alignment. The procedure will be as follows:

1. Identify enrolled patients scheduled to receive a verification CT scan.
2. Setup patient without the aid of holographic alignment (standard method).
3. Acquire verification CT scan.
4. Dismantle the setup.
5. Utilize holographic alignment to correct patient posture. This involves a therapist wearing the HoloLens 2 device and viewing the patient's reference hologram overlaid the patient. The therapist will manually adjust the patient to match the hologram.

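### Section 7 judges registration error by non-significance against one unsigned 3 mm value for both modalities, although the protocol's own proton tolerance is 2 mm

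*Combined protocol and SAP*

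**What the plan says.** Section 7.) Statistical Analysis states: "We will assess feasibility using a paired T-test". The hypothesis is that the mean paired differences in "registration error and registration time are not significantly different than 3 mm and 5 minutes". No split by modality, direction of subtraction, significance level or reason for 3 mm is given. The same bullet also plans estimation: "Mean estimates and associated 95% confidence intervals will be attained for registration error and registration time", for each method and for the paired difference.

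Section 4.) Background (MixR-Guided RT, after Table 1) judges the phantom results against two tolerances: "achieving less than the 5 mm alignment tolerance for 3D photon treatments" and "approaching the 2 mm alignment tolerance for proton treatments".

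Section 6.) Research Plan treats the modalities as two cohorts: "we intend to enroll 12 patients receiving either 3DCRT or IMRT and 12 patients receiving proton therapy". It gives an accuracy goal for photon only ("accuracy similar to or better than a traditional breast setup involving 3-point alignment (5mm tolerance"). It records the magnitude of the shift found at CBCT and says proton alignment is quantified in the same way. The main goal of the proton sub-aim is less setup time and less imaging dose. Registration error, time and imaging are joint primary endpoints for feasibility. Final position is set by IGRT. Sections 6 and 7 say that the study is an underpowered pilot and that its size was chosen for practicality.

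**The concern.** Two faults sit in one sentence.

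- **The form of the test.** Taken literally, a mean difference close to 3 mm supports feasibility and a mean difference close to zero speaks against it. Failure to reject is also not evidence of closeness.
- **The value.** The protocol measures proton alignment against 2 mm, yet allows a between-method difference of 3 mm. If MixRT's mean shift magnitude exceeds the comparator's by more than 2 mm, MixRT's own mean must exceed 2 mm, because the comparator's mean cannot be below zero.

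At stake is the accuracy statement for the proton cohort, in a pilot whose results are meant to support larger comparative studies and FDA clearance.

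**Working it through.** **Inputs from the documents**
- Benchmark for the paired difference: 3 mm (section 7).
- Tolerances: 5 mm photon, 2 mm proton (section 4).
- Proton cohort: n = 12 (section 6: "recruit an additional 12 patients scheduled to receive RT using a supine, pencil-beam scanning approach").
- Confidence level: 95% (section 7).

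**Assumptions**
- Two-sided 5% test, to match the planned intervals.
- One difference per patient, MixRT minus standard, in shift magnitude.
- SD of the paired differences: 1.4 mm, borrowed from the RMS row of Table 1. That is repeat scatter on a rigid phantom. The documents give no patient-level SD, so a range of 0.7 to 4.0 mm is shown.

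**The plan's own figures.** There is no power calculation to reproduce. The Table 1 RMS mean does reproduce: (2.4 + 2.6 + 3.3)/3 = 2.77, printed as 2.8. The 3 mm benchmark has no stated derivation.

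**Step 1: benchmark against tolerance.** 3/5 = 60% of the photon tolerance; 3/2 = 150% of the proton tolerance.

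**Step 2: literal reading** (pass if not significantly different from 3 mm). Half-width = t(0.975, 11) × SD/√n = 2.201 × 1.4/√12 = 0.89 mm. Observed means from 3 − 0.89 = 2.11 to 3 + 0.89 = 3.89 mm pass. The whole range lies above 2 mm whenever 2.201 × SD/√12 < 1, that is, SD below about 1.57 mm.

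**Step 3: ceiling reading** (pass if the upper 95% limit is below 3 mm). At SD 1.4 mm, observed means up to 2.11 mm pass. The chance of passing is the lower-tail probability of a noncentral t with 11 degrees of freedom and noncentrality (true difference − 3)/(SD/√12). At a true 2.5 mm this is −0.5/0.404 = −1.24, giving 20%. At a true 2.0 mm it is 62%.

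| SD (mm) | Literal: observed means that pass (mm) | Literal: P(pass), true 0 | Ceiling: P(pass), true 2.5 mm |
|---|---|---|---|
| 0.7 | 2.56–3.44 | 0.000 | 0.62 |
| 1.0 | 2.36–3.64 | 0.000 | 0.35 |
| 1.4 | 2.11–3.89 | 0.000 | 0.20 |
| 2.0 | 1.73–4.27 | 0.003 | 0.12 |
| 3.0 | 1.09–4.91 | 0.12 | 0.08 |
| 4.0 | 0.46–5.54 | 0.34 | 0.06 |

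Under the literal reading a true 3 mm worsening passes 95% of the time at any SD. Under the ceiling reading, tighter data pass a true 2.5 mm more often, so the margin is at fault and not only the sample size.

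**Step 4: does changing 3 to 2 suffice?** No. Under the literal test at SD 1.4 mm, a true 2.5 mm passes 0.795 of the time against 3 mm and 0.795 against 2 mm, because it lies 0.5 mm from each.

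**Step 5: both changed.** With an upper-limit rule and a 2 mm margin at SD 1.4 mm, observed means up to 2 − 0.89 = 1.11 mm pass. The chance of passing is 99% at a true 0, 2.5% at 2.0 mm and 0.1% at 2.5 mm.

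**Step 6: if the modalities were pooled** (n = 24, SD 1.4 mm), the half-width is 0.59 mm. The literal range is 2.41 to 3.59 mm, and the ceiling rule passes observed means up to 2.41 mm.

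**The case against.** The best case for the plan has four parts.

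- **The proton aim is not mainly about accuracy.** Its stated main goal is time and imaging dose, and feasibility draws on three measures together. This stands. A reader might infer that the proton decision rests on the 3 mm value; the documents do not say so. Registration error is nevertheless a joint primary endpoint and is formally tested.
- **IGRT sets the final position.** This also stands. A reader might infer that patients could be treated out of tolerance, and nothing in the documents supports that. The issue concerns the shift found at first imaging. Section 7 does not say whether proton registration error is that shift or the residual after correction; a 3 mm allowance on a residual would be harder still to defend.
- **Means and 95% intervals are planned for each method.** If they were given by modality, the MixRT proton mean could be read directly against 2 mm. That would help, but section 7 neither splits by modality nor ties the intervals to a decision.
- **It is an acknowledged pilot.** That excuses low power. It does not excuse a decision rule that rewards a 3 mm difference over none.

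Two stronger readings are also tempting. One takes the 80% pass rate at a true 2.5 mm as the cost of using 3 mm where the tolerance is 2 mm. Step 4 shows that it comes from the test form and is the same against either value. The other holds that 3 mm is sound for photon because it lies inside 5 mm. That compares a difference with an absolute tolerance: if the 3-point shift averages more than 2 mm, a 3 mm difference puts MixRT beyond 5 mm.

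**Conclusion.** The concern holds for the accuracy component of the proton feasibility conclusion. Section 7 uses one unsigned 3 mm value for both modalities, treats non-significance as support, and has no proton criterion tied to the 2 mm tolerance. At n = 12 and SD 1.4 mm, every observed mean difference that passes the literal rule exceeds 2 mm, and a true difference of zero almost never passes. Under the more charitable ceiling reading, a true 2.5 mm worsening passes about 20% of the time.

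These sizes rest on the assumed SD, on a MixRT-minus-standard sign that the plan does not state, and on separate analysis by modality. The contradiction between 3 mm and 2 mm, and the fault in the test form, do not depend on the SD. The revision should be made; it does not call into question delivered position or the proton cohort's time and imaging goals.

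**What to change.** In section 7:

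1. Define the difference as MixRT minus standard in first-CBCT shift magnitude, and analyse it separately for photon and proton.
2. Replace the non-significance rule with an upper-limit criterion: the upper 95% confidence limit must lie below a stated margin for that modality. The proton margin should be no larger than the protocol's own 2 mm tolerance. The photon margin should be justified against the section 6 goal of matching or improving on 3-point alignment, and not kept at 3 mm by default.
3. Compare each method's mean shift and 95% interval with the section 4 tolerance. Report by method the share of fractions with a first-CBCT shift within 2 mm (proton) or 5 mm (photon). This is needed because a margin on the difference, even 2 mm, does not by itself place MixRT within tolerance when the comparator's own shift is above zero.

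**Cost.** SAP wording and one summary table from data already collected; no added scans, visits or patients. The proton accuracy criterion becomes harder to meet. With a 2 mm margin and no true difference, it passes 99% of the time at SD 1.4 mm, 88% at SD 2.0 mm and 56% at SD 3.0 mm.
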